9.3 Variables

- Demographic data: Gender, age, race (if allowed as per local regulation)
- Other Baseline Assessments: Weight
- Medical history, including MS, malignancies, severe and opportunistic infections
- MS-Medication history: DMD, immunosuppressive/immunomodulatory agents (other than DMD, such as corticosteroid treatment)
- Therapy with Cladribine Tablets [date of administration and number of tablets taken versus prescribed dose (treatment adherence)]
- Reason for switching from first line DMD to Cladribine Tablets
- Participation in a Cladribine Patient Support Program
- Course of disease
 - o Relapses
 - o MRI data
 - T2, T1 Gd+ and CUA lesion counts
 - o EDSS Score
 - o T25FW (time in seconds, optional)
 - o 9-HPT (time in seconds, optional)
- TSQM-v1.4 VAS score
- MSIS-29 score

- · EQ-5D-3L score
- Safety (Serious Adverse Events (SAEs), Adverse Events of Special Interest (AESI) and Adverse Drug Reactions (ADRs))

Derived and transformed data needed for the analysis are described in Section 9.7.2.

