- Patients with history of alcohol or drug abuse that could potentially interfere with their participation in the study.
- 3. Patient that have received Cladribine in the past
- Concurrent participation in an investigational study in which patient assessment and/or treatment may be dictated by a protocol

Outcomes

Primary Endpoint

Difference in ARR between the pre-baseline 12-month period and over the 12 months period before End of Study follow-up (2 years).

Secondary Endpoints

 Difference in ARR between the pre-baseline 12-month period and over the 12 months period after start of cladribine (1 year)

Cladribine

	 Percentage of patients with 6-month disability progression (EDSS, T25FW, 9-HPT)² at the end of the study follow-up period (2 years).
	 Percentage of patients with 6-month disability improvement (EDSS, T25FW, 9-HPT)² at the end of the study follow-up period (2 years).
	 Occurrence of adverse events and of serious adverse events.
	 Quality of life (MSIS-29), Treatment Satisfaction (TSQM v1.4) and CCI
	 Treatment adherence, assessed as percentage of cladribine tablets taken versus prescribed dose
Variables	Demographics
	Medical History
	MS history
	Prior and current MS medication
	Reason for switching from first line DMD to Cladribine tablets
	 Therapy with Cladribine Tablets (date of administration and number of tablets taken versus prescribed dose)
	 Participation in a Cladribine Patient Support Program
	Relapse Count: ARR
	 Disability test: EDSS, Timed 25-Foot Walk, 9-Hole Peg Test (EDSS Plus)
	 Quality of life questionnaire: MSIS-29
	• CCI
	Treatment Satisfaction Questionnaire: TSQM v1.4

² Disability progression is defined as progression on ≥1 of 3 components (EDSS, T25FW, and/or 9HPT) confirmed ≥24 weeks apart and with a ≥20% minimum threshold change for T25FW and 9HPT. Progression on EDSS is defined as at least 1 point in the EDSS score or an increase of at least 1.5 points if the baseline EDSS score is 0. Disability Improvement is defined as improvement on ≥1 of 3 components (EDSS, T25FW, and/or 9HPT) confirmed ≥24 weeks apart and with a ≥20% minimum threshold change for T25FW and 9HPT. Improvement on EDSS is defined as a decrease in EDSS by at least 1 point (1.5 points if baseline EDSS was 1.5). T25FW and 9HPT are optional and will be performed if done as per routine practice.

	Safety [Serious Adverse Events (SAEs), Adverse Events of Special Interest (AESI) and Adverse Drug Reactions (ADRs)]

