9.1.2.2 Secondary

- Difference in ARR between the pre-baseline 12-month period and over the 12 months period after the start of cladribine (1 year)
- Percentage of patients with 6-month disability progression⁵ at the end of the study followup period (2 years), measured as EDSS, T25FW (optional) and 9-HPT (optional).

⁴ Relapses will be diagnosed by the treating physicians, as per routine clinical practice; a typical definition within this context is the appearance of new symptoms of the exacerbation of pre-existing symptoms that are attributed to MS and occur over a minimum of 24 hours and separated from a previous attack by at least 30 days, in the absence of fever or infection.

⁵ Disability progression is defined as progression on ≥1 of 3 components (EDSS, T25FW, and/or 9HPT) confirmed ≥24 weeks apart and with a ≥20% minimum threshold change for T25FW and 9HPT, Progression on EDSS is defined

L04AA40 MS700568 0070

Cladribine

- Percentage of patients with 6-month disability improvement⁴ at the end of the study followup period (2 years), measured as EDSS, T25FW (optional) and 9-HPT (optional)
- · Occurrence of adverse events and of serious adverse events
- Quality of life (MSIS-29)
- Treatment Satisfaction (TSQM v1.4)
- CCI
- Treatment adherence, assessed as percentage of cladribine tablets taken versus prescribed dose

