patient have been made. If a subject is lost to follow-up, every possible effort must be made by study center personnel to contact the subject and determine the reason for discontinuation. The measures taken to follow-up must be documented. If a subject discontinues before completion of study procedures, the reason for discontinuation must be documented in the case report form (CRF) and source documents.

Safety data assessment

Safety events are collected throughout the study as described in Section 11.5.

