- · Bacterial, viral, fungal, parasitic and protozoal infections
- Severe and/or serious infections will be defined by their management or their outcome: all
 infections that result in death or hospitalisation or require the use of intravenous treatment
 (e.g. antibiotics)
- Opportunistic infections are defined as an invasive infection caused by microorganisms that
 are normally non-pathogenic or rarely pathogenic in individuals with normal immune
 function or cause an infection of a type or severity not seen in the normal host; opportunistic
 infections exclude herpetic infection
- Herpes zoster (not considered an opportunistic infection). Only severe and/or serious herpes zoster will be collected.

The duration of infections will be the difference between start date and recovery date as reported by the treating physician.

Patients may contribute more than I episode to this analysis if, after resolution as defined, another infection occurs.

Severe lymphopenia: Any occurrence of severe (or worse) lymphopenia during the study period, classified as Grade ≥ 3. As per the Common Terminology Criteria for Adverse Events (CTCAE) (v4.03: June 14, 2010) from the National Institutes of Health, the grades of lymphopenia are defined based on laboratory test results that indicate a decrease in number of lymphocytes in a blood sample:

- Grade 3 (severe lymphopenia): <500 200/mm³; <0.5 0.2 x10⁹ /L
- Grade 4 (serious lymphopenia): <200/mm³; <0.2 x 10⁹ /L

Duration of severe lymphopenia: It is defined as the interval from the finding of severe lymphopenia until resolution, which is the achievement of a CTCAE Grade I [ranging from the

lower limit of normal (LLN) to 800/mm³] or normalization (above LLN i.e. normal lymphocyte count or CTCAE Grade 0). Patients may contribute more than 1 episode to this analysis if, after resolution as defined, severe lymphopenia occurs again. The frequency of lymphocyte counts in patients with severe lymphopenia will be described with special emphasis on the number and timing of lymphocyte counts in relation to Cladribine tablets dosing and during episodes of severe lymphopenia.

Events not to be considered as Adverse Events

Medical conditions present at study start, that do not worsen in severity or frequency during the study are defined as Baseline Medical Conditions and are NOT to be considered AEs.

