11.4 Recording of Adverse Events

The recording period for AEs begins, when the subject is initially included in the study (date of signature of first informed consent) and continues at least end of the mandatory safety-follow-up period at last study visit. However, as enrollment may take place from the time of cladribine prescription up until the second treatment week, in the first treatment year, any ADRs assessed as related to cladribine by the Investigator after the first dose of cladribine but before signature of Informed Consent must be recorded in the eCRF as well.

All adverse events, as specified above, occurring during the study, must be documented by the Investigator in the eCRF, including its description, seriousness, severity (grading), duration (onset

and resolution dates), causal relationship, any other potential causal factors, actions taken with the study drug (e.g. dose reduction, withdrawal), required treatment and outcome of the AE.

Note - Event term 'Death', 'Disability' and 'Hospitalization'

Death, disability, and hospitalization are considered outcomes in the context of safety reporting and not usually considered ARs/AEs. Therefore the primary cause of death, disability or hospitalization should be recorded and reported as an SAE/AR, and the outcome should be recorded in a separate data field. However, a term for the outcome will be selected if it is the only information reported or provides significant clinical information.

If death occurs, the primary cause of death or event leading to death should be recorded and reported as an SAE. "Fatal" will be recorded as the OUTCOME of this respective event and not be as separate event. Only, if no cause of death can be reported (for example, sudden death, unexplained death), the death per se might then be reported as an SAE.

Reports of Special Situations (see definition) are also to be recorded in the CRF following the AE procedure, even if occurring without AE.

Pregnancy and Breastfeeding. Pregnancy or breastfeeding must be recorded in the CRF and additionally be reported to the Sponsor immediately (within 24 hours of awareness) by using separate paper data collection forms for pregnancy, independent if an AE was reported or not. The outcome of the pregnancy should be followed up and reported to the Sponsor until delivery.

Women who become pregnant under therapy with Cladribine tablets should discontinue treatment.

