11.5 Safety Data Collection for Reporting

Safety data collection forms:

The following safety data collection forms are used in this study:

- (Serious) Adverse Event Report Form
- Pregnancy Report Form (paper form)
- Parent-Child/Foetus AE Report Form (paper form)
- Adverse Event of Special Interest (AESI) Report Form

Reportable events:

The following events are reportable to the Safety Check Desk at CRO within 24 hours of awareness:

- All SAEs (related or unrelated) are to be reported independent of their relationship to the study drug via the eCRF or using back-up paper forms in case of eCRF outage
- AEs of special interest (AESI) are to be reported via the eCRF or using back-up paper forms in case of eCRF outage

CONFIDENTIAL

- Pregnancy or lactation is to be reported by using the paper Pregnancy Report Form.
- All events that occur in a Child/Foetus of a pregnant woman who was exposed to the study drug are to be reported by using the paper Parent-Child/Foetus Report Form

Special situations (see definition) should be reported by using the paper (Serious) Adverse Event Report Form by indicating whether serious or not

Non-serious ADRs are to be reported within 4 calendar days via the eCRF or using the paper (Serious) Adverse Event Report Form in case of eCRF outage.

Procedure for Safety Data Reporting (completion and forwarding):

For any new events that are listed in the section above "Reportable events", the Investigator/HCP will report the event by transmitting the Safety Data Collection Form in English via the eCRF or via paper (as described in the section above) to the Sponsor via CRO Safety Check Desk. The Investigator must respond to any request by CRO for follow-up information, as noted above for initial report. CRO should forward the follow-up information within 24 hours to Global Patient Safety, as noted above for initial reports. The sponsor has to meet strict regulatory timelines associated with expedited safety reporting obligations.

The data entered on the safety data collection forms must be consistent with the information recorded in the eCRF. If some data are missing, the form should be completed with the available data and a follow-up report will be sent as soon as possible. The minimum information to be included in the initial report is the following:

- Investigator name and contact details
- Subject identification (e.g., ID number, gender, age)
- Product (including lot/ batch number)

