#### 15.1.1 All Adverse Events

The AEs will be summarized using the latest version of MedDRA PT as event category and MedDRA primary SOC body term as body system category.

Incomplete AE-related dates will be handled as specified in Section 9.8.1.

The following tables will be created

- TEAE summary table with the number and percentage of patients having:
  - o TEAE
  - TEAE of Special Interest (TEAESI)
  - TEAE leading to death
  - o TEAE leading to Cladribine dose reduction
  - o TEAE leading to Cladribine temporary discontinuation
  - o TEAE leading to Cladribine permanent discontinuation
  - TEAE leading to study termination
  - TEAE not recovered/resolved
  - Any serious TEAE:
    - TEAESI
    - Leading to death
    - Leading to Cladribine dose reduction

- Leading to Cladribine temporary discontinuation
- Leading to Cladribine permanent discontinuation
- Leading to study termination
- Not recovered/resolved
- Cladribine related TEAE:
  - TEAESI
  - Serious
  - Leading to death
  - Leading to Cladribine dose reduction
  - Leading to Cladribine temporary discontinuation
  - Leading to Cladribine permanent discontinuation
  - Leading to study termination
  - Not recovered/resolved
- Incidence of TEAE by Primary SOC and PT
- Incidence of Serious TEAE by Primary SOC and PT
- Incidence of Serious TEAE related to Cladribine by Primary SOC and PT
- Incidence of TEAE leading to Cladribine temporary discontinuation Primary SOC and PT
- Incidence of related TEAE leading to Cladribine temporary discontinuation Primary SOC and PT
- Incidence of TEAE leading to Cladribine permanent discontinuation Primary SOC and PT
- Incidence of related TEAE leading to Cladribine permanent discontinuation Primary SOC and PT
- Incidence of TEAE leading to death by Primary SOC and PT
- Incidence of related TEAE leading to death by Primary SOC and PT
- Incidence of TEAE by Primary SOC and PT and relationship to Cladribine
- Incidence of TEAE by Primary SOC and PT and severity
- Incidence of TEAESI by Primary SOC and PT and severity
- Incidence of TEAESI by Primary SOC and PT and by relationship to Cladribine

2.0

• Incidence of Serious TEAESI by Primary SOC and PT and by relationship to Cladribine

All AEs regardless of being treatment-emergent or not will be listed.

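### The protocol gives two scopes for adverse event collection, so it is not settled what the TEAE tables count

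*Protocol*

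**What the plan says.** **Narrow scope.** Protocol 9.3 lists "Safety (Serious Adverse Events (SAEs), Adverse Events of Special Interest (AESI) and Adverse Drug Reactions (ADRs" and no other class of event. The variables row of the abstract (Section 4) says the same: "Safety [Serious Adverse Events (SAEs), Adverse Events of Special Interest (AESI) and Adverse Drug Reactions (ADRs". The safety paragraph of 9.2.4 reads "Safety events are collected throughout the study as described in Section 11.5". Section 11.5 then names SAEs whatever their relationship, AESIs, pregnancy or lactation, events in an exposed child or foetus, and special situations. It adds one further non-serious class: "Non-serious ADRs are to be reported within 4 calendar days via the eCRF". The safety-reporting entry in SAP Appendix 18.1 (potential protocol deviations) names ADRs, AESIs, SAEs and the pregnancy and child forms. It does not mention failure to record other AEs.

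**Wide scope.** The secondary endpoint in 9.1.2.2 is "Occurrence of adverse events and of serious adverse events". Section 11.1 defines an AE without regard to causality. Section 11.4 states "All adverse events, as specified above, occurring during the study, must be documented by the Investigator in the eCRF", with seriousness, severity and causal relationship for each. SAP 15.1.1 tabulates all TEAEs by SOC and PT, by severity, and as "Incidence of TEAE by Primary SOC and PT and relationship to Cladribine".

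**Herpes zoster.** Within the AESI infection categories, 11.1 says "Herpes zoster (not considered an opportunistic infection). Only severe and/or serious herpes" zoster is to be collected.

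SAP Section 7 declares no change from the protocol and does not settle the scope.

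**The concern.** Safety at two years is a stated secondary objective, and its endpoint is the occurrence of adverse events. Under the narrow scope, a non-serious event outside the AESI list reaches the database only if the investigator judges it related. A table headed TEAE would then be a table of SAEs, AESIs and ADRs. Overall incidence would be too low. The share of patients with a TEAE whose event is related would be too high, simply because of the entry rule. The same tables feed both interim analyses (SAP Appendix 18.2 lists 15.3.1.1, 15.3.1.2 and 15.3.1.11).

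**Working it through.** The plan states no AE rate, so there is no figure to reproduce. The check sets the scope statements side by side for each class of event.

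| Event class | 9.3 and abstract | 9.2.4 via 11.5 | 11.4, endpoint, SAP 15.1 |
|---|---|---|---|
| Serious, related or not | in | in | in |
| AESI, any seriousness or relationship | in | in | in |
| Non-serious, non-AESI, related | in (ADR) | in (ADR) | in |
| Non-serious, non-AESI, unrelated | not listed | no entry | in |

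Only the last row differs. It follows that:

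- **Unchanged:** serious-TEAE and TEAESI tables.
- **Nearly unchanged:** related-TEAE tables. The exceptions are related zoster that is neither severe nor serious, if the 11.1 sentence is read as a limit on collection, and events with relationship missing, which SAP 15.1 counts as related.
- **Changed:** any TEAE; TEAE by SOC/PT; TEAE by severity; the not-related part of the by-relationship table; and summary rows such as not recovered, or leading to discontinuation, where the event belongs to the last row.

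**Illustration, with every rate assumed.** SAP 15.1 counts patients, so the illustration does too. Let *p* be the share of patients with an SAE, AESI or ADR. Let *q* be the share of the remaining patients who have only events from the last row. Narrow incidence = *p*; wide incidence = *p* + (1 − *p*)*q*. With N = 242 (Protocol 9.5), rounded to whole patients:

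| *p* | Narrow | Wide, *q* = 10% | Wide, *q* = 40% |
|---|---|---|---|
| 20% | 48/242 = 19.8% | 68/242 = 28.1% | 126/242 = 52.1% |
| 35% | 85/242 = 35.1% | 100/242 = 41.3% | 148/242 = 61.2% |
| 50% | 121/242 = 50.0% | 133/242 = 55.0% | 169/242 = 69.8% |

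For relationship, assume *p* = 35% and that 25% of all patients have a related TEAE. The related share among patients with any TEAE is 0.25/0.35 = 71.4% under the narrow scope. Under the wide scope it is 0.25/0.415 = 60.2% (*q* = 10%) or 0.25/0.61 = 41.0% (*q* = 40%). Patients with only not-related events go from 0.35 − 0.25 = 10.0% of all patients to 16.5% or 36.0%.

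These figures show the direction of the effect and how strongly it depends on *q*. They are not estimates for this study.

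**The case against.** The best defence is that the operative text favours the wide scope. Section 11.4 is the recording rule. It adds related reactions occurring before consent as an extra, so recording after consent must be wider than ADRs. Section 11.3 defines a not-related category and requires an alternative explanation for it. Section 11.5 is about reporting and sets deadlines, so its list can properly be shorter than the recording list. This is a good argument for which scope was probably intended, but it does not remove the conflict. Section 9.3 is the list of study variables, not of reportable events, and 9.2.4 says events are collected, not reported, as in 11.5. The back-reference in 11.4 to what was specified earlier could mean the AE definition or the classes listed after it.

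A reader might also infer four stronger points, which the documents do not support:

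- *That 9.3 drops every non-serious, unrelated event.* It keeps AESIs whatever their seriousness or relationship, for example Grade 3 or higher lymphopenia and any malignancy.
- *That non-serious zoster is excluded outright, so a site is told both to report a related case and not to collect it.* The sentence sits inside the AESI definition and most naturally limits AESIs only. It also keeps severe cases, and the infection definition there includes need for intravenous treatment. Only zoster that is neither severe nor serious is in doubt.
- *That sites will differ in what they record.* The eCRF and its completion instructions are not in the documents and may impose one reading. If practice were mixed, pooling without a site factor (SAP 9) would not reveal it.
- *That a definite fraction of events will be lost.* No document gives a rate from which to calculate one.

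**Conclusion.** The inconsistency is real. The abstract, 9.3, and 9.2.4 with 11.5 state one scope; 11.4, the endpoint and the SAP state another. The two differ for exactly one class: events that are non-serious, unrelated and not of special interest. Under the narrow scope, any-TEAE incidence, TEAE by SOC/PT and by severity, and the not-related counts are understated. The direction follows from the entry rule, but the size cannot be derived from the documents. The conclusion does not depend on sites disagreeing. If all follow the narrow scope, the endpoint and tables are mislabelled; if all follow the wide one, the abstract, 9.3 and 9.2.4 are wrong. The effect is confined to a descriptive secondary safety endpoint and does not touch the primary analysis. It should be corrected.

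**What to change.** State one scope in the abstract, 9.1.2.2, 9.2.4, 9.3, 11.4, 11.5, the SAP and its deviation list.

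- **Preferred:** change the abstract and 9.3 to all AEs. Make 9.2.4 refer to 11.4 for recording, and say that 11.5 governs expedited reporting only. Add unrecorded AEs to the deviation list. The cost is wording, plus some extra AE entry at any site that has recorded only the narrow classes.
- **If the narrow scope is intended:** relabel the endpoint and the TEAE tables, including the interim outputs, as SAEs, AESIs and ADRs, and do not present them as overall AE incidence. The by-relationship table can stay under that label, because SAEs and AESIs still divide into related and not related. The cost is wording and table titles, and the study gives up an estimate of overall AE incidence.
- **In either case:** say in 11.1 that the herpes zoster sentence limits only what is reported as an AESI, so that zoster that is neither severe nor serious follows the general AE/ADR rule.

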9.4 Data Source

The data to be collected in the study will be obtained by means of an (e)CRF. The data in the (e)CRF should be consistent with the relevant source documents. Further details are provided in Section 9.6.

Patients will complete the MSIS-29, EQ-5D-3L and TSQM v1.4 questionnaires at the sites and the information will be transcribed into the eCRF by the investigator site staff. Patients can complete the MSIS-29 and EQ-5D-3L remotely at baseline when remote consent is performed and authorized in the country.

Pre-baseline data, listed in Section 9.2.4, will be obtained from patient records and will be transcribed into the eCRF by the investigator site staff.

